6.12.4.2. Systemic Hypersensitivity Reaction

The number and proportion of patients experiencing treatment-emergent potential systemic hypersensitivity reactions will be summarized and compared by treatment group using Fisher's exact test. The following Standardised MedDRA Query (SMQ) will be used to identify potential systemic hypersensitivity reactions from all TEAEs:

- Anaphylactic reaction (SMQ). Besides using the narrow and broad terms designated within the SMQ, the following search algorithm will also be implemented as another approach to determine if a patient had an anaphylactic reaction: if a patient (had at least 1 event in Category A) or (had at least 1 event that is in category B and also had at least 1 event that is in category C) or (had at least 1 event that is in category D and [also had at least 1 event in category B or at least 1 event in category C]).
- Angioedema (SMQ)
- Hypersensitivity (SMQ)

Specifically, need to perform the following: (1) any narrow or algorithmic term from any 1 of the 3 SMQs indicated above (that is, combined search across narrow and algorithmic portions of all 3 SMQs); (2) any narrow scope term within each SMQ, separately (that is, narrow SMQ search); (3) any term within each SMQ, separately (that is, broad SMQ search); (4) narrow scope term search within each SMQ, report the PT nested within each SMQ.

A similar summary will be provided using the TEAEs reported by the investigator as possibly related to study drug.

Note that an individual patient may contribute multiple events. Also, a single event may satisfy multiple SMQs, in which case the event contributes to every applicable SMQ.

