The number and percentage of patients who experienced an SAE, including deaths and SAEs temporally associated or preceding deaths, will be summarized by treatment group using MedDRA PT (without regard to SOC). Events will be ordered by decreasing frequency within SOC. A listing of all SAEs will also be provided.

The number and percentage of patients who discontinued from study due to an AE will be summarized by treatment group using MedDRA (without regard to SOC) using all data regardless of IP use. The number and percentage of patients who discontinued IP due to an AE will be also summarized by treatment group using MedDRA PT (without regard to SOC) using data prior to discontinuation of IP. Events will be ordered by decreasing frequency. A listing of all AEs as reason for study or IP discontinuation will also be provided.

The number and percentage of patients who experienced other notable TEAEs (potential systemic hypersensitivity reaction, injection site reaction, and hepatic disorder) will be summarized by treatment group using all TEAEs regardless of IP use.

For events that are gender-specific (as defined by MedDRA), the denominator and computation of the percentage will include only patients from the given gender.

[Table 6.5](#) summarizes the planned analyses and the requirement of analysis data for different analysis periods. A 'Yes' in the IP USE column indicates that only data collected prior to discontinuation of IP will be included.

Table 6.5. Treatment-Emergent Adverse Event Analysis Periods

Analysis Period	Analysis Population	Analysis	IP USE	Treatment
Lead-in Period	All enrolled patients	AE overview; TEAE by PT, SAE, discontinuation from study due to AE	N/A	Open-label insulin lispro
Treatment Period (0-26 Weeks)	All patients in safety population	AE overview; TEAE by SOC and by PT; common TEAE; TEAEs by maximum severity; SAE; discontinuation from IP due to AE	Yes	LY900014, insulin lispro, LY900014+20
Treatment Period (0-26 Weeks)	All patients in safety population	AE overview; TEAE by SOC; common TEAE; SAE; discontinuation from study due to AE; other notable AEs	All data regardless of IP use	LY900014, insulin lispro, LY900014+20
Treatment Period (0-52 Weeks)	All patients with double-blind treatment in safety population	AE overview; TEAE by SOC and by PT; common TEAE; TEAEs by maximum severity; SAE; discontinuation from IP due to AE	Yes	LY900014, insulin lispro

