Week 0 – 26 + Visit 801	All patients with open-label treatment in safety population (excluding Japan)	AE overview; TEAE by SOC; common TEAE; SAE; other notable AEs	All data regardless of IP use	LY900014+20
Week 0 – 52 + Visit 801	All patients with double-blind treatment in safety population	AE overview; TEAE by SOC; common TEAE; SAE; discontinuation from study due to AE; other notable AEs	All data regardless of IP use	LY900014, insulin lispro

Abbreviations: AE = adverse event; IP = investigational product; N/A = not applicable/available; PT = Preferred Term; SAE = Serious Adverse Event; SOC = System Organ Class; TEAE = treatment-emergent adverse event.

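### The anaphylaxis search algorithm in SAP 6.12.4.2 pairs events from different categories with no onset window, so unrelated events months apart can add noise to the algorithmic count and the combined search

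*SAP*

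**What the plan says.** SAP 6.12.4.2 searches three Standardised MedDRA Queries (SMQs), which "will be used to identify potential systemic hypersensitivity reactions from all TEAEs". For the anaphylactic reaction query, in addition to its narrow and broad terms, "the following search algorithm will also be implemented as another approach to determine if a patient had an anaphylactic reaction". There are three routes:

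- one category A event;
- the patient "had at least 1 event that is in category B and also had at least 1 event that is in category C";
- the patient "had at least 1 event that is in category D and [also had at least 1 event in category B or at least 1 event" (the sentence closes by naming C as the alternative to B).

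Four outputs follow. The first is a combined search that takes "any narrow or algorithmic term from any 1 of the 3 SMQs indicated above". The other three are narrow terms by query, all terms by query, and narrow preferred terms nested within each query. Patient counts "will be summarized and compared by treatment group using Fisher's exact test". A similar summary is limited to events that the investigator reported as possibly related to study drug.

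SAP 6.12.2 adds that the notable events, including potential systemic hypersensitivity, "will be summarized by treatment group using all TEAEs regardless of IP use". In its Table 6.5, the row for Week 0-52 plus Visit 801 in the double-blind arms lists "AE overview; TEAE by SOC; common TEAE; SAE; discontinuation from study due to AE; other notable AEs", again on all data regardless of IP use.

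**The concern.** Every condition in the algorithm is met by the patient having had an event at some point in the analysis period. An anaphylactic reaction is a single episode, and the two-category routes make sense only if the findings occur together. Read literally, a category B event in Week 3 and an unrelated category C event in Week 44 make the patient an anaphylaxis case. So do a B event on IP and a C event well after the last dose, because patients who stop IP early are asked to complete the remaining visits (Protocol 5.3.1).

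These patients enter the algorithmic count and the combined search. For a rare reaction, a few chance cases per arm could match or outnumber the real ones and make a true difference between LY900014 and insulin lispro harder to see in those two outputs.

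**Working it through.** **Is there a timing rule anywhere?** No onset window, same-episode condition or adjudication step for these events was found in either document. The SAP does handle timing elsewhere. Section 6.12.4.1 merges hypoglycemia entries that are 30 minutes or less apart, and 6.12.4.4.3 reviews how close transaminase and bilirubin elevations are in time. The possibly-related summary filters on relatedness, not on time.

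**How far apart can paired events be?** Visit 801 is at Week 56 for the double-blind arms, so the longest period is 56 × 7 = 392 days; the 26-week period is 182 days. If onsets are independent and uniform, chance pairs separate as follows.

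| Period | More than 7 days apart | More than 28 days apart |
|---|---|---|
| 0-26 weeks | 92% | 71% |
| 0-52 weeks + Visit 801 | 96% | 86% |

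**How many chance cases?** The plan states no figure to reproduce.

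- Taken from the documents: n = 436 per double-blind arm (Protocol 10.1).
- Assumed, because the documents give nothing: period incidences pB, pC and pD, and independence between categories.

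Without a window, a patient qualifies by chance with B and C together, or with D and exactly one of B or C:

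E = n × [pB·pC + pD·(pB + pC − 2·pB·pC)]

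With onsets within ±1 day over 364 days, the chance that a given pair matches is about 3/364 = 0.0082. Adding the three possible pairs gives an upper bound:

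E(window) = n × (pB·pC + pD·pB + pD·pC) × 3/364

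| pB, pC, pD | No window | ±1 day |
|---|---|---|
| 3%, 3%, 1% | 436 × 0.001482 = 0.65 | 436 × 0.0015 × 3/364 = 0.005 |
| 5%, 5%, 2% | 436 × 0.0044 = 1.92 | 436 × 0.0045 × 3/364 = 0.016 |
| 10%, 5%, 2% | 436 × 0.0078 = 3.40 | 436 × 0.008 × 3/364 = 0.029 |
| 10%, 10%, 2% | 436 × 0.0136 = 5.93 | 436 × 0.014 × 3/364 = 0.050 |

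Both columns cover the B+C and D routes, so they compare like with like. Using 392 days (3/392) leaves the windowed range at about 0.005 to 0.05. If B and C were each only 2%, the B+C route alone would give 436 × 0.0004 = 0.17.

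**The case against.** The strongest reply is that this is a screen. The section's output is labelled as potential reactions, and the algorithm is one approach beside others. For a rare, serious event it is defensible to favour sensitivity. Narrow terms by query and nested preferred terms are reported without any pairing, and the possibly-related summary should remove many unrelated events. All serious events are listed (SAP 6.12.2) and have narratives (6.12.8). A tight window could lose a true case recorded as separate symptoms with inexact dates. All of this stands. It limits the harm and shapes the fix, but it does not supply the missing timing rule.

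A reader might infer more than the documents support:

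- **That the counts are dominated by coincidental pairs.** At the low end the excess is below one patient per arm. A patient already caught by a narrow term adds nothing to the combined search. Every incidence used here is assumed.
- **That a false difference between arms is likely.** Chance pairs arise in every arm, and the double-blind arms have the same planned duration. With equal background rates, Fisher's exact test keeps its error rate, so what remains is noise.
- **That all hypersensitivity results are contaminated.** Only the algorithmic count, the combined search and their possibly-related counterparts use the pairing. The antibody-status subgroup analysis in SAP 6.12.7.1 does not say which hypersensitivity definition it uses.
- **That the SAP departs from the standard query.** The documents do not show whether that query carries its own window.

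**Conclusion.** The concern holds as a specificity weakness in one safety search. Followed as written, the rule classes patients with unrelated, widely separated events as having had an anaphylactic reaction and puts them into a comparison between arms. Under the stated assumptions the excess is about 0.6 to 5.9 patients per double-blind arm, against about 0.005 to 0.05 with a ±1 day link. The size rests entirely on assumed incidences and independence; the missing timing condition does not. The consequence is noise that may dilute a real difference in the affected outputs. The separate narrow, broad and preferred-term searches and the primary and multiplicity-adjusted analyses are untouched. The change is worth making because it is cheap and makes the algorithmic count interpretable.

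**What to change.** In SAP 6.12.4.2:

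- Define the B-with-C and D-with-B-or-C routes by episode: the paired events must have onset within a short, prespecified window. Same day or within one calendar day is an example; the sponsor should choose and justify the interval.
- Use that count in the combined search and in the possibly-related summary.
- Leave category A and the narrow and broad searches unchanged.
- Report the unrestricted algorithmic count as a sensitivity screen, and list the onset dates of the paired events for every patient it flags.
- Treat partial onset dates as meeting the window, so that true cases are not lost.

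The cost is a few lines of SAP text, a comparison of adverse event start dates and one listing. The remaining downside is that a true case with a wrongly recorded date could drop out of the windowed count; the unrestricted count and listing limit that risk.

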6.12.4.3. Injection Site Reaction

The injection site reactions will be searched by MedDRA PTs from all TEAEs. The number and percentage of patients experiencing treatment-emergent injection site reaction will be summarized and compared by treatment group using Fisher's exact test.

For injection site reactions, the presence and severity of erythema, induration, pain, pruritus, and edema were collected through the eCRF, and will be summarized for each treatment. There will be no statistical comparison between treatments.

6.12.4.4. Hepatobiliary Events

6.12.4.4.1. *Treatment-Emergent Potential Hepatic Disorder*

The percentages of patients with treatment-emergent drug-related hepatic disorder events will be summarized and compared by treatment group using MedDRA PT nested within each SMQ ordered by decreasing frequency. The following SMQs based on MedDRA will be used to identify potential hepatic disorders:

- broad and narrow terms in the Liver related investigations, signs and symptoms SMQ (20000008)
- broad and narrow terms in the Cholestasis and jaundice of hepatic origin SMQ (20000009)
- broad and narrow terms in the Hepatitis non-infections SMQ (20000010)
- broad and narrow terms in the Hepatic failure, fibrosis and cirrhosis and other liver damage SMQ (20000013)
- narrow terms in the Liver-related coagulation and bleeding disturbances SMQ (20000015)

The percentage of patients with any 1 of the terms will be summarized in addition to the percentages for each MedDRA PT. The percentages of patients with potentially drug-related hepatic disorders that led to permanent study treatment discontinuation will be summarized similarly.

6.12.4.4.2. *Liver Enzyme and Bilirubin Lab Values*

The liver enzyme measures (alanine aminotransferase [ALT], aspartate aminotransferase [AST], alkaline phosphatase [ALP], direct bilirubin, total bilirubin) will be summarized by treatment group. Postbaseline value and the change from baseline (last nonmissing value before randomization) to postbaseline value at Week 26 visit (planned tests) will be summarized for patients who have both a baseline and at least 1 postbaseline result, and compared between treatment groups by using ANCOVA model with the term of treatment and baseline value of the response variable. All analyses will be provided in both SI and CN units.

The last nonmissing observation at or prior to Week 26 (including early discontinuation visit) will also be analyzed by an ANCOVA model with the term of treatment, baseline value of response variable.

The analyses for Week 52 will be similar to that described above using data for the 2 double-blind treatment groups.

6.12.4.4.3. Treatment-Emergent Elevation of Liver Enzyme Lab Values

The percentages of patients with the following elevations in hepatic laboratory tests at any time during the treatment period (0 to 26, 0 to 52 weeks) will be summarized between treatment groups:

- The percentages of patients with postbaseline ALT measurement ≥ 3 times (3X), 5 times (5X), and 10 times (10X) the Covance upper limit of normal (ULN) will be summarized for all patients with a postbaseline value by the following baseline categories: $\leq 1X$, $>1X$ to $<3X$, $\geq 3X$, missing.
- The percentages of patients with postbaseline AST measurement ≥ 3 times (3X), 5 times (5X), and 10 times (10X) the Covance ULN will be summarized for all patients with a postbaseline value by the following baseline categories: $\leq 1X$, $>1X$ to $<3X$, $\geq 3X$, missing.
- The percentages of patients with postbaseline total bilirubin measurement ≥ 2 times (2X) the Covance ULN will be summarized for all patients with a postbaseline value by the following baseline categories: $\leq 1X$, $>1X$ to $<2X$, $\geq 2X$, missing.

Baseline will be the maximum observation in the baseline period including the lead-in period. The maximum value will be the maximum value from the treatment period. Planned and unplanned tests will be included.

Graphical profiles of ALT, AST, total bilirubin, and ALP will be provided for patients with an ALT or AST $\geq 3X$ ULN or total bilirubin $\geq 2X$ ULN during the treatment period. A listing for these patients will also be provided, including the actual measurement of ALT, AST, ALP, and total bilirubin, the corresponding reference high limits, demographics, disposition, drug exposure and AEs. The review for these patients includes an assessment of the proximity of any ALT or AST elevation to any total bilirubin elevation, ALP levels, other potential causes, and the temporal association with events such as nausea, vomiting, anorexia, abdominal pain, or fatigue.

All patient data, regardless of whether on IP, will be used for the above analyses related to hepatobiliary events.

6.12.5. Clinical Laboratory Evaluation

The data from safety laboratory measures will be summarized at Week 26 where the lab test is planned to be collected. Postbaseline and change from baseline to postbaseline for laboratory tests will be summarized for patients who have both baseline and at least 1 postbaseline result and compared between treatment groups by using ANCOVA model with the term of treatment and baseline value of the response variable. Analyses will be provided in both SI and CN units.

The last nonmissing observation at or prior to Week 26 (planned tests including early discontinuation) will also be analyzed by an ANCOVA model with the term of treatment, baseline value of the response variable.

The analyses for Week 52 will be similar to that described above using data for the 2 double-blind treatment groups.

The percentages of patients with treatment-emergent abnormal, high, or low laboratory results at any time during the treatment period (0 to 26, 0 to 52 weeks) will be summarized for patients who have both baseline and at least 1 postbaseline result and compared between treatment groups using Fisher's exact tests. A treatment-emergent abnormal result is defined as a change from normal at all baseline visits to abnormal at any time during the treatment period. A treatment-emergent high result is defined as a change from a value less than or equal to the high limit at all baseline visits to a value greater than the high limit at any time during the treatment period. A treatment-emergent low result is defined as a change from a value greater than or equal to the low limit at all baseline visits to a value less than the low limit at any time during the treatment period. Planned and unplanned measurements will be included. Covance reference ranges will generally be used to define the low and high limits. Only patients who have normal baseline values for the analysis being performed will be included in the analysis for treatment-emergence.

Liver enzymes measures will not be included in the above analyses as different analyses will be used as described in Section 6.12.4.4.2 and Section 6.12.4.4.3.

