- ALT or AST >3X ULN with the appearance of fatigue, nausea, vomiting, right upper-quadrant pain or tenderness, fever, rash, and/or eosinophilia (>5%).
- alkaline phosphatase (ALP) >3X ULN.
- ALP >2.5X ULN and TBL >2X ULN.
- ALP >2.5 ULN with the appearance of fatigue, nausea, vomiting, right upper-quadrant pain or tenderness, fever, rash, and/or eosinophilia (>5%).

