9.4.6. Safety Monitoring

Lilly will periodically review evolving aggregate safety data within the study by appropriate methods.

If a study patient experiences elevated ALT $\geq 3X$ ULN, ALP $\geq 2X$ ULN, or elevated TBL $\geq 2X$ ULN, clinical and laboratory monitoring should be initiated by the investigator. Details for hepatic monitoring depend upon the severity and persistence of observed laboratory test abnormalities. To ensure patient/patient safety and comply with regulatory guidance, the investigator is to consult with the Lilly CRP regarding collection of specific recommended clinical information and follow-up laboratory tests. See [Appendix 4](#).

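### The SAP takes alkaline phosphatase out of the treatment-emergent laboratory analysis and does not put it into the hepatic threshold counts or the listing criteria

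*SAP*

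**What the plan says.** Three SAP sections have to be read together.

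- SAP 6.12.4.4.2 sets the scope: "The liver enzyme measures (alanine aminotransferase [ALT], aspartate aminotransferase [AST], alkaline phosphatase [ALP], direct bilirubin, total bilirubin) will be summarized by treatment group". Each of these is summarised and "compared between treatment groups by using ANCOVA model with the term of treatment and baseline value of the response variable". No threshold appears in this section.
- SAP 6.12.5 defines treatment-emergent abnormal, high and low results for laboratory tests, then closes with "Liver enzymes measures will not be included in the above analyses as different analyses will be used", referring to 6.12.4.4.2 and 6.12.4.4.3.
- SAP 6.12.4.4.3 is the only categorical hepatic laboratory analysis. Its three items are "The percentages of patients with postbaseline ALT measurement" at 3X, 5X and 10X ULN, "The percentages of patients with postbaseline AST measurement" at the same multiples, and total bilirubin at 2X ULN. It then states "Graphical profiles of ALT, AST, total bilirubin, and ALP will be provided for patients with an ALT or AST" at or above 3X ULN, or total bilirubin at or above 2X ULN. The listing covers the same patients. It shows their ALP, but ALP is not a criterion for being listed.

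The protocol does use ALP. Section 9.4.6 (the sentence beginning "If a study patient experiences elevated ALT") starts hepatic monitoring on ALT ≥3X, ALP ≥2X or total bilirubin (TBL) ≥2X ULN. Section 8.1.1 has seven hepatic conditions under which the investigator, after consulting the medical monitor, is to consider stopping investigational product (IP). Four name ALT or AST. Three name ALP, the simplest being "alkaline phosphatase (ALP) >3X ULN".

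**The concern.** The liver measures are removed from one categorical analysis on the ground that others will be used, but for ALP and direct bilirubin no other categorical analysis exists. A patient whose only abnormality is an ALP above 3X ULN meets a protocol condition for considering discontinuation, yet is in no laboratory shift count, elevation count, profile or listing. The safety comparison of chemistry measures (objective 17, which is exploratory) would then give no patient count for the analyte on which the protocol bases its three non-transaminase conditions.

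A related mismatch sits wholly in the protocol. The monitoring sentence in 9.4.6 leaves out AST, while 8.1.1 names AST in four conditions, one of which depends on how long the elevation lasts.

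**Working it through.** The plan states no figure to reproduce, so the check compares rules. Each of the seven conditions in Protocol 8.1.1 was split by analyte into single routes: five through ALT, five through AST and three through ALP, 13 in all. Each route was set just above its own threshold with the other analytes at 1X ULN. It was then tested against the SAP 6.12.4.4.3 entry rule (ALT or AST ≥3X, or TBL ≥2X) and the Protocol 9.4.6 trigger (ALT ≥3X, ALP ≥2X or TBL ≥2X).

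| Protocol 8.1.1 condition (multiples of ULN) | Opens SAP profile and listing? | Starts 9.4.6 monitoring? |
|---|---|---|
| ALT or AST >8X | Yes | ALT yes; AST alone no |
| ALT or AST >5X for over 2 weeks | Yes | ALT yes; AST alone no |
| ALT or AST >3X, with TBL >2X or prothrombin time >1.5X | Yes | ALT yes; AST with TBL yes, through bilirubin; AST with prothrombin time no |
| ALT or AST >3X with symptoms or eosinophilia | Yes | ALT yes; AST no |
| ALP >3X | **No** | Yes |
| ALP >2.5X with TBL >2X | Yes, through bilirubin only | Yes |
| ALP >2.5X with symptoms or eosinophilia | **No** | Yes |

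**SAP side.** Two of seven conditions (2 of 13 routes) do not open the listing, and both are ALP conditions. None of the three ALP conditions has a count based on ALP.

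**Protocol side.** All ALP routes start monitoring. Four of the 13 routes do not, and all four are AST without raised bilirubin.

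**What the continuous analysis can show.** Protocol 10.1 plans 436 patients per double-blind arm. As an illustration, suppose 5 of them rise from 1X to 3X ULN. The arm mean moves by 5 × (3 − 1)/436 = 0.023X ULN. The documents give no standard deviation for ALP, so whether that shift would be detected cannot be computed; the example shows only that it is small. SAP 6.1 also reports the maximum, so the largest analysed value per arm would be visible. The maximum does not say how many patients were high or who they were. SAP Table 6.2 also limits the continuous laboratory analyses to planned tests, whereas 6.12.4.4.3 includes unplanned ones. An ALP peak found on an unplanned test would therefore miss the maximum too.

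**AST follow-up.** In the Schedule of Activities, the chemistry panel after Visit 8 falls only at Visits 18 and 22 and at early discontinuation. No scheduled test, and no test triggered by 9.4.6, assures a repeat within the time frame of the over-2-weeks condition when AST alone is raised.

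**The case against.** The strongest reply is that ALP is not neglected. SAP 6.12.5 refers to both hepatic subsections, and 6.12.4.4.2 does analyse ALP, with a maximum as well as a mean. Section 6.12.4.4.1 compares arms on hepatic adverse event queries that include cholestasis and liver investigations. Adverse events leading to discontinuation are tabulated, listed and given narratives (SAP 6.12.2 and 6.12.8). Cholestasis with TBL ≥2X ULN is counted and listed through bilirubin.

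Much of this stands, and it rules out several stronger readings that a reader might infer:

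- That all three ALP conditions escape the listing. The one combined with bilirubin does not.
- That a cholestatic imbalance could not appear at all. The adverse event route could show one. It depends on reporting, however, and Protocol 9.4.5 requires reporting of clinically significant laboratory findings that lead to a diagnosis, not of every threshold crossing.
- That the 8.1.1 conditions are mandatory stopping rules. They are conditions for considering discontinuation.
- That the AST duration condition could never be assessed. Investigators must document their review of each laboratory report (Protocol 9.2), and Appendix 4 allows follow-up tests, AST included, for any treatment-emergent hepatic abnormality. What is missing is an assured repeat.
- That no open-label patient has chemistry after Visit 18. Under SAP 5.1, open-label patients in Japan follow the 52-week schedule. For the others, IP ends at Visit 18, so a later AST value could not bear on stopping it.

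None of this supplies a count or a patient-level display for ALP laboratory values. The SAP does not leave ALT, AST or bilirubin to adverse event reporting, and it gives no reason to treat ALP differently.

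**Conclusion.** The point holds as a specific, limited gap. ALP is expressly excluded from the general categorical analysis and absent from the one meant to replace it. Its laboratory values get continuous summaries, including the maximum, and ANCOVA only. The size is two of seven protocol conditions not reaching the listing and three of seven without an ALP-based count. This rests on reading the specific exclusion in 6.12.5 as overriding the general chemistry row in SAP Table 6.2, which sets only population and baseline. Direct bilirubin falls into the same gap, but no protocol condition uses it, so it matters less.

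The AST mismatch is a separate question of protocol consistency. The SAP already counts and lists AST. No view is taken here on which protocol passage is right.

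**What to change.** In SAP 6.12.4.4.3:

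1. Add the percentages of patients with postbaseline ALP at the cut-offs already in the protocol (≥2X ULN from 9.4.6; >2.5X, >3X, and >2.5X with TBL >2X from 8.1.1). Present them by baseline category, as is done for the other analytes, with planned and unplanned tests included.
2. Add ALP at the protocol's existing monitoring cut-off (≥2X ULN) to the criteria for the profiles and listing.
3. Optionally, return direct bilirubin to the treatment-emergent analysis in 6.12.5.

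The central laboratory panel already collects these data, so the cost is programming and a few more table and listing rows. If the SAP can no longer be revised, SAP 6.1 allows the change and its justification to be described in the clinical study report.

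Separately, the sponsor should reconcile Protocol 9.4.6 with 8.1.1 on AST. No clinical rule or threshold is proposed.
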